## Cardiac Resonance Imaging (CMR) Assessment of New Left Atrial (LA) Fibrosis

### ***Baseline CMR to quantify baseline atrial fibrosis***

[figure not shown]
Quantification of LA fibrosis will be obtained using methods previously described. The LA wall will be segmented manually and regions of fibrosis in CMR images will be defined by an intensity threshold determined by expert inspection. Fibrotic tissue is detected when its enhancement is one-to-five standard deviations above the mean of normal tissue intensity. A 3D LA fibrosis map will be created using Corview Volume Rendering Software (Marrek Inc., Salt Lake City, UT). Inter-observer and intra-observer reproducibility for these techniques have been previously reported. Fibrosis will be represented as the volumetric percentage of left atrial wall enhancement.

### ***Three-month CMR to visualize ablation-induced scars***

Quantification of LA ablation induced scarring with CMR has been previously described. 3-months post-ablation, endocardial and epicardial borders of the LA wall are contoured manually and blood pooling or other artifacts are omitted in scanned images. Pixel intensities are distributed as bimodal to distinguish normal from injured tissue. Pixels with lower intensities are chosen as normal tissue and ablation-induced lesions are defined at one to five standard deviations above the mean of normal tissue pixel intensity. The assessment of ablation induced scars is best before or at 3 months after the procedure. The lower threshold used in the later scans causes weak scar lesions to be detected and an inexperienced eye might mistake them for new fibrosis. Regions marked as the ablation lesion will be independently evaluated by two blinded experts to ensure correctness.

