#### **2) Progression of left atrial fibrosis**

Monitoring will start at the baseline CMR scan prior to ablation and up to the end of the clinical trial.

Defined as:

- a) The percentage (%) of new fibrosis seen on the 12-month CMR scan compared to CMR scans taken at baseline and at 3-months post-ablation.

The primary endpoints will be compared between the treatment (dronedarone) and control arms (placebo) respectively.

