### ***Twelve-month CMR to assess for new fibrosis formation***

After segmentation and measurement of LA fibrosis on pre-ablation scans and on 3-month post-ablation scans, we will use the latter as baseline for our trial to see if any new enhancement has formed or regressed (Figure 3). Transient post-ablation lesions will be defined as enhancements detected on the first post-ablation scan but not in the second post-ablation scan. New fibrosis will be defined as enhancement detected on the second post-ablation scan and absent on the first post-ablation scan. Both of these parameters will be reported as the percentage of total LA area.

**Figure 3:** There is new enhancement detected on the post-ablation MRI of the left atrium. New fibrosis is displayed in green. The red area represents ablated regions. Adapted from Kheirkhahan et al.

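### The plan says later scans are read at a lower threshold and sets no common cut for the 3- and 12-month scans, so unchanged tissue can count as new fibrosis in a co-primary endpoint

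*Combined protocol and SAP*

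**What the plan says.** All of this is in the combined protocol and SAP.

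- **Endpoint.** Under Primary Endpoints, item 2, the fibrosis co-primary is the percentage "of new fibrosis seen on the 12-month CMR scan compared to CMR scans taken at baseline and at 3-months post-ablation".
- **Reference scan.** The twelve-month CMR section names the 3-month scan: "we will use the latter as baseline for our trial to see if any new enhancement has formed or regressed".
- **Rule.** The same section states: "New fibrosis will be defined as enhancement detected on the second post-ablation scan and absent on the first post-ablation scan". The result is reported as a percentage of total LA area. No threshold is given for the 12-month reading.
- **Baseline threshold.** The baseline CMR section says that "regions of fibrosis in CMR images will be defined by an intensity threshold determined by expert inspection", and gives a range: "Fibrotic tissue is detected when its enhancement is one-to-five standard deviations above the mean of normal tissue intensity".
- **3-month threshold.** The three-month CMR section uses the same range: "ablation-induced lesions are defined at one to five standard deviations above the mean of normal tissue pixel intensity".
- **Later scans.** That section then adds: "The lower threshold used in the later scans causes weak scar lesions to be detected". It warns that an inexperienced reader could take these lesions for new fibrosis.
- **Safeguards.** Two blinded experts independently check the regions marked as ablation lesion (three-month CMR section). CMR readers do not have access to treatment arm (Blinding).

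**The concern.** A subtraction between two scans measures change only if both are read on the same scale. Here the plan says the later reading uses a lower threshold, and the 12-month scan is the only one scheduled after month 3. A piece of wall whose intensity relative to normal tissue has not moved, but which lies between the two cuts, is absent at 3 months and detected at 12. The rule scores it as new fibrosis.

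The plan names this hazard for weak scar, yet states nothing that takes it out of the endpoint. The expert check applies to regions already marked as lesion. Weak scar below the 3-month cut was never marked, so the check does not reach it.

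What is at stake is the meaning of a co-primary endpoint, and both co-primaries must succeed for the trial to be positive. A percentage of new fibrosis that contains faint ablation scar cannot be read as disease progression. The analysis section also models change in percentage fibrosis across the three scans, and a falling threshold would feed into that as well.

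**Working it through.** **1. The plan's own figure.** Inputs from Sample Size Estimation: control mean progression 10%, relative reduction 20%, SD 1.59, two-sided alpha 0.05, 20% dropout. Allocation is 1:1.

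- Planned difference = 0.20 × 10 = 2.0 points.
- 86 randomized × 0.8 is about 34 per arm. SE = 1.59 × √(2/34) = 0.386, and power = Φ(2.0/0.386 − 1.96) = 0.999. The stated power above 99% is reproduced.
- 330 × 0.8 = 264, or 132 per arm. SE = 1.59 × √(2/132) = 0.196, and power is about 1.00. This is also reproduced.

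Neither calculation contains a term for a threshold that differs between scans.

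**2. What the rule does to unchanged tissue.** Let k3 and k12 be the cuts at 3 and 12 months, in SDs above the normal-tissue mean, with k12 < k3. Tissue at constant relative intensity z is scored as new whenever k12 < z < k3. This follows from the definition alone.

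**3. Possible size.** The documents give no values for k3 or k12. Assume, for illustration, Gaussian normal-wall intensity that is identical on both scans. The share of unchanged normal wall scored as new is sf(k12) − sf(k3), where sf is the upper normal tail. The fourth column assumes the artefact is added to a true 10% and 8%, treating percent of normal wall as percent of LA area. The difference then stays at 2.0 points and the measured relative reduction is 2.0/(10 + artefact).

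| 3-month cut | 12-month cut | Scored as new | Measured relative reduction |
|---|---|---|---|
| 2 SD | 1 SD | 15.87% − 2.28% = 13.6% | 2.0/23.6 = 8.5% |
| 3 SD | 2 SD | 2.28% − 0.13% = 2.1% | 2.0/12.1 = 16.5% |
| 4 SD | 3 SD | 0.135% − 0.003% = 0.13% | 2.0/10.13 = 19.7% |

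All these cuts lie inside the 1 to 5 SD range that the plan gives for the baseline and 3-month scans.

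**4. Effect on power.** Suppose instead that a share f of the assumed 10% is artefact that the drug cannot change. The difference becomes 2.0 × (1 − f). An artefact that varies between patients with SD s raises the total SD to √(1.59² + s²). With 132 per arm:

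| f | s | Difference | Total SD | Power |
|---|---|---|---|---|
| 50% | 0 | 1.0 | 1.59 | 0.999 |
| 75% | 0 | 0.5 | 1.59 | 0.72 |
| 0 | 3 | 2.0 | 3.40 | 0.998 |
| 0 | 5 | 2.0 | 5.25 | 0.87 |
| 50% | 3 | 1.0 | 3.40 | 0.67 |
| 50% | 5 | 1.0 | 5.25 | 0.34 |

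Power drops materially only when the artefact makes up most of the measurement or varies widely between patients. The documents establish neither.

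**The case against.** **The 12-month section itself states no threshold.** The lower threshold appears in one explanatory sentence, which can be read as the reason for mapping scar at 3 months. This stands in part: the actual 12-month cut is not known. But that sentence is the plan's only statement about thresholds on later scans, and nothing in the subtraction rule corrects for it.

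**The cited imaging methods may fix the cut or handle scar.** They are cited for the baseline and 3-month readings and cannot be checked here. If they settle the matter, the sponsor can say so.

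**The plan speaks only of weak scar and an inexperienced reader.** Also fair. Extending the problem to other unchanged wall is an inference from the subtraction rule.

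**A reader might infer that the planning SD and the power collapse.** The documents do not support this. A threshold difference common to all patients shifts both arm means and largely cancels in the arm contrast. It adds variance only if the cut varies between patients. Under the Gaussian assumption a 0.25-SD change in the cut moves the reading by 0.25 × the normal density: 1.35 points at 2 SD and 3.24 points at 1.5 SD. Taken as independent added SDs, these give totals of √(1.59² + 1.35²) = 2.09 and √(1.59² + 3.24²) = 3.61. Power with 132 per arm is then about 1.00 and 0.994. The plan also does not say where 1.59 comes from, so it may already contain reading variability.

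**A reader might also infer a bias towards dronedarone.** CMR readers do not see treatment arm, and nothing in the plan points to a differential error.

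**One fixed multiple for every patient would override the plan's expert-set threshold.** That is debatable, and the point does not need it. It needs only the same cut on both scans of the same patient.

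**Conclusion.** The point holds as a defect in the endpoint definition. Followed as written, the plan can put tissue of unchanged relative intensity, including the weak scar it names, into the new-fibrosis co-primary, and the stated review does not remove it.

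The size cannot be derived from the documents. Under the Gaussian assumption it runs from 13.6% of normal wall (cuts of 2 then 1 SD) through 2.1% (3 then 2 SD) to about 0.1% (4 then 3 SD), against a planned difference of 2.0 points. It may be negligible if the core lab works at high cuts.

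Given reader blinding, the error should be mostly non-differential. It inflates both arm means, dilutes the relative reduction and clouds what the endpoint measures. The stated power is reproduced, and its loss is not shown unless the artefact dominates or varies widely between patients. Type I error is not the issue.

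**What to change.** In the three-month and twelve-month CMR sections, before any 12-month scan is read for the endpoint:

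- For the new-fibrosis subtraction, apply the same SD multiple to both post-ablation scans of a patient, normalised to each scan's own normal-tissue mean and SD, with readers blinded to arm. One way is to re-threshold the stored 3-month segmentation at the 12-month cut. Normalising by scan matters because the CMR Protocol section allows 1.5T or 3T scanners and more than one contrast agent.
- Let the 3-month scar map keep its own threshold, and exclude regions mapped as ablation scar from new fibrosis.
- Repeat the subtraction at one alternative common multiple as a sensitivity analysis.

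The cost is a paragraph of text and some reprocessing by the core lab; the plan already stores segmentations and images. The downside is that the 3-month cut used in the subtraction is no longer tuned separately. A common cut also does not remove random scan-to-scan noise: with fully independent noise in the same Gaussian model, a common 2-SD cut still labels 0.0228 × 0.9772 = 2.2% of normal wall as new. The change removes the systematic threshold artefact only. If the core lab already uses a common cut, it is enough to state that and correct the sentence about later scans.

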### ***Twelve-month CMR to assess for new fibrosis formation***

After segmentation and measurement of LA fibrosis on pre-ablation scans and on 3-month post-ablation scans, we will use the latter as baseline for our trial to see if any new enhancement has formed or regressed (Figure 3). Transient post-ablation lesions will be defined as enhancements detected on the first post-ablation scan but not in the second post-ablation scan. New fibrosis will be defined as enhancement detected on the second post-ablation scan and absent on the first post-ablation scan. Both of these parameters will be reported as the percentage of total LA area.

**Figure 3:** There is new enhancement detected on the post-ablation MRI of the left atrium. New fibrosis is displayed in green. The red area represents ablated regions. Adapted from Kheirkhahan et al.

## **Statistical Methods, Data Analysis, and Interpretation**

---

This is a prospective, randomized clinical trial to assess whether dronedarone is superior to placebo in decreasing AF recurrence and to SOC in reducing the progression of fibrosis after AF ablation.

### **A. Sample Size Estimation**

#### ***Atrial Fibrosis Progression***

Based on the assumption that the mean progression of fibrosis in the control group is 10%, the SD for the progression of fibrosis is 1.59. Predicting a 20% dropout rate, 86 randomized patients will provide >99% power with a 2-sided  $\alpha= 0.05$  to detect a reduction of 20% in fibrosis progression between dronedarone and the control arm. Given that an estimated 330 patients will be recruited, the study will have approximately 100% power to detect the group difference in atrial fibrosis progression.

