Based on our preliminary data, dronedarone appears to have the potential to slow down the progression of cardiac fibrosis, with multiple mechanisms of action hypothesized. One of the main speculated mechanisms of action has been derived from pre-clinical publications and is based on dronedarone preventing vascular alterations that participate in structural remodeling and atrial maintenance substrate. Oxidative stress (ROS) generated in the myocardium promotes endothelial to mesenchymal transition (EndMT) by reducing endothelial nitric oxide (NO) production. Numerous studies have shown that ROS and EndMT are major contributors towards cardiac fibrosis. Circulating symmetric dimethylarginine (SDMA), a biomarker that reduces the synthesis of NO, is also associated with increase in atrial wall thickness in AF. Dronedarone stimulates nitric oxide synthase (NOS) which increases the bioavailability of NO, and reduces SDMA, playing a critical role in preserving the epithelial phenotype. In fact, there is an improvement in global antioxidant status after treatment with dronedarone.

Furthermore, a decrease in collagen deposition in the atria has been observed after treatment with dronedarone, thereby improving atrial structure, decreasing wall thickness, and slowing down the development of cardiac fibrosis. Finally, during episodes of AF, factors known to induce atrial fibrosis growth such as, collagen-1 and fibronectin-1, are released into atrial tissues. For this reason, rhythm control by means of AADs Class III may serve to limit the amount of time available for these biomarkers to disperse into atrial tissues as well as, proactively managing fibrosis progression.

[figure not shown]
[figure not shown]
Preliminary data from [name] team at the University of Utah (Salt Lake City, UT) assessing fibrosis progression in AF patients (n = 17) that received standard of care (SOC) (n = 8) or dronedarone (Multaq®, n=9), are presented in Figure 2. Patients underwent two MRIs over

Page 10 of 49

Version 4.0:  
Revision Date: April 27th, 2022

Copyright© April 2022 Tulane University School of Medicine,  
All rights reserved

**Figure 1:** Cumulative incidence of stroke by Utah Stage of LA fibrosis. Adapted from King et al.

**Figure 2:** Mean fibrosis at baseline and follow-up by randomized treatment group. Preliminary data from the University of Utah.

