TULANE  
University  
Arch Organization

the course of a median 365.5 days [IQR: 290-382] as part of their care. In the SOC group, they observed a 10% progression of fibrosis, whereas in the dronedarone group, there was only a 4.5% progression over this period. Dronedarone slowed atrial fibrosis progression by more than 50% relative to the SOC group. This reduction is clinically relevant, as each 1% increase in atrial fibrosis from baseline is associated with a 6% higher risk of AF recurrence after ablation. Although underpowered due to the small sample size, a trend is apparent between baseline and follow-up MRIs, and it appears as though vast differences exist. With an increased sample size, we may see more significant effects.

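### The fibrosis SD of 1.59 has no stated source and conflicts with the protocol's own pilot, so fibrosis and overall power should be shown over a range of SDs

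*Combined protocol and SAP*

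**What the plan says.** Under Statistical Methods, A. Sample Size Estimation, the fibrosis paragraph takes a control mean of 10% and states that "the SD for the progression of fibrosis is 1.59". With 20% dropout and two-sided alpha 0.05, it says that "86 randomized patients will provide >99% power" for a 20% reduction, and that with 330 recruited "the study will have approximately 100% power to detect the group difference in atrial fibrosis progression". The next subsection, on atrial arrhythmia (AA) recurrence, requires both co-primary endpoints to be positive for success. It gives AA recurrence 86% power with 138 events and treats fibrosis power as close to 100%. From these it concludes that overall power is at least 85%.

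The only fibrosis progression data by treatment are in the Background: a pilot "assessing fibrosis progression in AF patients (n = 17) that received standard of care (SOC) (n = 8) or dronedarone" (n = 9). Its two scans were taken over "the course of a median 365.5 days [IQR: 290-382] as part of their care". The result reads: "In the SOC group, they observed a 10% progression of fibrosis, whereas in the dronedarone group, there was only a 4.5% progression". The protocol's comment on it is: "Although underpowered due to the small sample size, a trend is apparent between baseline and follow-up MRIs". The text gives no SD, confidence interval or p-value for the pilot.

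**The concern.** The planning control mean of 10% equals the pilot's standard-of-care mean, which suggests, without proving it, that the pilot informed the planning. If so, the planning SD should be compatible with the pilot. An SD of 1.59 is very small beside a 5.5-point difference between arms. Even with 8 and 9 patients, that difference would be overwhelming evidence and not a trend.

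The overall power of the success criterion is at stake. The plan carries the AA recurrence power over unchanged as the joint power, and that step is valid only if fibrosis power is practically 100%. Whether it is depends on one SD that the reader cannot check. AA recurrence drives the sample size, so N itself is not in question.

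**Working it through.** **Inputs.** Control mean 10, relative reduction 20% (difference 2 points), SD 1.59, dropout 20%, two-sided alpha 0.05, 1:1 allocation, N = 330, AA power 86% (all from Sample Size Estimation and Randomization). Pilot n = 8 and 9, means 10 and 4.5 (Background). Power is from the two-sample t-test (noncentral t), with noncentrality = difference / (SD x sqrt(2/n per arm)).

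**1. The plan's own figures.**
- 86 randomized: 86 x 0.8 / 2 = 34 evaluable per arm; noncentrality 2 / (1.59 x sqrt(2/34)) = 5.19; power 99.9%.
- 330 randomized: 330 x 0.8 / 2 = 132 per arm; noncentrality 2 / (1.59 x sqrt(2/132)) = 10.2; power about 100%.

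Both statements reproduce.

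**2. What SD 1.59 would mean in the pilot**, if its figures are change scores on the same scale.
- Between arms: SE = 1.59 x sqrt(1/8 + 1/9) = 1.59 x 0.486 = 0.773; t = 5.5 / 0.773 = 7.12 on 15 df; p = 3.5e-6.
- Within arm, paired: 10 / (1.59/sqrt(8)) = 17.8 and 4.5 / (1.59/sqrt(9)) = 8.5.

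**3. SD at which the pilot's between-arm p equals 0.05.** 5.5 / (2.131 x 0.486) = 5.31. A larger p needs a larger SD: 6.5 for p = 0.10 and 8.4 for p = 0.20. Under this reading 5.3 is therefore a lower bound.

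**4. Trial power over the SD**, for a 2-point difference and 132 per arm. The joint figure is 0.86 x fibrosis power, which assumes independence. The bounds hold under any dependence: fibrosis power + 0.86 - 1, up to the smaller of the two powers.

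| SD | Fibrosis power | Joint, independent | Joint, any dependence |
|---|---|---|---|
| 1.59 | about 100% | 86% | 86% |
| 3.8 | 99% | 85% | 85% to 86% |
| 4.5 | 95% | 82% | 81% to 86% |
| 5.3 | 86% | 74% | 72% to 86% |
| 6.5 | 70% | 60% | 56% to 70% |
| 8 | 53% | 45% | 39% to 53% |

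**5. Where the stated claims stop holding.** The claim of more than 99% with 86 randomized fails above an SD of about 1.9. The claim of at least 85% overall fails above about 3.8.

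**6. At the pilot's own difference.** With 5.5 points, 132 per arm and SD 5.3, fibrosis power is above 99.99%.

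**The case against.** The strongest reply is that the conflict with the pilot is indirect. The trend is described between baseline and follow-up scans, and the Figure 2 caption reads "Mean fibrosis at baseline and follow-up by randomized treatment group", so the comparison may have been of fibrosis levels and not of changes. An unpaired comparison of levels would be non-significant in the standard-of-care group once the between-patient SD of level exceeds about 9.3 (10 / (2.145 x sqrt(2/8))), and in the dronedarone group above about 4.5. This reading cannot be excluded, but it barely rescues 1.59: with a level SD of 9.3, a change SD of 1.59 needs a scan-to-scan correlation of 1 - 1.59²/(2 x 9.3²), about 0.985. Alternatively, the word underpowered could refer to the planned 2-point effect, for which the pilot had 68% power at SD 1.59. That does not account for calling a 5.5-point difference a trend.

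Three further points stand. Figure 2 is not shown and may give a spread. The pilot scans were about a year apart as part of care, which is not the post-ablation 3-to-12-month contrast described for new fibrosis. And the plan has slack: the overall claim survives an SD 2.4 times the planned one (3.8 / 1.59), and the 2-point target is well below the pilot's 5.5 points.

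A reader might infer that the sample size arithmetic is wrong, that the true SD is 5.3 or more, or that 1.59 is really a standard error (1.59 x sqrt(8) or sqrt(9) would give an SD of 4.5 to 4.8). The documents support none of these as a conclusion. The arithmetic reproduces, 5.3 is the boundary of an inferred test, and the standard-error explanation cannot be verified from the text.

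**Conclusion.** The point holds as a matter of an unsupported input that conflicts with the protocol's own pilot. A missing citation alone would be a documentation gap; the conflict makes it worth correcting. The unqualified statements on fibrosis power and overall power are not supported as they stand. If the SD is about 5.3, fibrosis power for the planned effect is 86% and joint power about 74%; at 8 they are 53% and 45%.

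This rests on reading the pilot figures as changes on the same scale as the planning mean, on a non-significant between-arm result, on a 2-point difference, and on 20% loss. The joint figures also take the stated 86% AA power at face value, so a lower AA power would reduce all of them.

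A reader might go further and conclude that the trial is too small for the fibrosis endpoint. That does not follow: joint power stays at 85% or more up to an SD of about 3.8, and at the pilot's difference fibrosis power is near 100% even at SD 5.3. The derivation of the 138 events before loss and the differing descriptions of the scan interval are separate issues and are not settled here.

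**What to change.** Trace 1.59 to its source. Confirm that it is the SD of per-patient change, on the same scale as the 10% mean and over a named scan interval, and not, for example, a standard error or a value in another unit. Correct it if it is not, and reconcile it with the pilot description. Replace the three flat power statements with a short table of fibrosis and joint power for SDs from about 1.6 to 8. State the dependence assumption behind the joint figure and that it is conditional on the AA recurrence power.

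The cost is one recalculation and a few revised sentences. N, conduct and analysis do not change. The downside is that the stated power may look less favourable.
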